Using the parameters identified, the ultimate sample size for each treatment arm is as many as 45 patients in the mITT population. The stopping rules (rejection regions), expressed as number of responses per patients treated, are 0/10, 1/14, 2/18, 3/22, 4/26, 5/29, 6/32, 7/35, 8/37, 9/39, 10/41, 11/43, 12/44, and 13/45. Thus, if more than 13 responses are observed among the first 45 patients enrolled who meet the criteria for the mITT population, the drug will be declared efficacious. If the true ORR is 20% (null hypothesis), the probability of early termination during the study is 0.92, and the expected sample size prior to termination is 28 patients; the Type 1 error equal to 0.0499 and Power equal to 0.9065. If the true ORR is 40% and $N=45$, the exact 95% confidence interval (Clopper-Pearson) around the point estimate for ORR will be (25.7; 55.7).

If the outcome is promising and the option is taken to enroll an additional number of patients up to 100 in the mITT population in a specific treatment arm to increase the size of the safety database and narrow the confidence interval around the ORR point estimate, the 95% confidence interval around a true ORR of 40% will be (30.3; 50.3). Data collected in patients enrolled beyond the planned Phase 2 sample size will be used in secondary and supportive analyses.

For the purpose of making decisions for continued enrollment and for conduct of the final analysis for the Phase 2, the mITT population is defined as all patients who receive at least one dose of MGCD265.

Table 1: Pre-screening Assessments

To establish potential eligibility for future enrollment into Study 265-109, pre-screening for tumor genotype may be performed in advance of anticipated clinical screening for study entry, e.g., during treatment with chemotherapy required prior to study entry.

	Guidance
Informed Consent for Tumor Genotyping Pre-screening	Informed consent must be obtained prior to sending tumor tissue or blood for Sponsor-approved local or central laboratory genotyping. The informed consent form and process may be performed in accordance with documented institutional practice or using the study-specific, IRB-approved pre-screening ICF. An IRB/EC approved process for obtaining consent from patients who are remotely located may be used.

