9.1 Hypothesis and Sample Size

This Phase 2, parallel-arm study will use a Bayesian Predictive Probability Design (Lee-2008) that minimizes the number of patients enrolled to test the hypothesis. The design will be applied separately and using the same assumptions in each of four treatment arms. As many as 45 patients are planned for inclusion in the primary analysis for each treatment arm. The study also provides for the addition of up to 55 patients to each of two treatment arms to provide sufficient safety and/or efficacy data to support an accelerated approval market application in two study populations. Thus, the ultimate sample size for this study could include as many as 290 patients.

ORR in accordance with RECIST v1.1 is the primary endpoint. With currently available treatments, ORR is assumed to be 20% (p_0), thus this rate is considered uninteresting. The target ORR using MGCD265 in this study is 40% (p_1). The trial will monitor the number of observed responses continuously after evaluating the first on-study disease assessments of the first 10 patients in each treatment arm in the mITT population. In creating the statistical design, the Type 1 error (α) is constrained to < 0.05 and Power ($1-\beta$) is constrained to ≥ 0.90 .

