Using the parameters identified, the ultimate sample size for each treatment arm is as many as 45 patients in the mITT population. The stopping rules (rejection regions), expressed as number of responses per patients treated, are 0/10, 1/14, 2/18, 3/22, 4/26, 5/29, 6/32, 7/35, 8/37, 9/39, 10/41, 11/43, 12/44, and 13/45. Thus, if more than 13 responses are observed among the first 45 patients enrolled who meet the criteria for the mITT population, the drug will be declared efficacious. If the true ORR is 20% (null hypothesis), the probability of early termination (under H_0) during the study is 0.92 and the expected sample size prior to termination is 28 patients. The Type 1 error is equal to 0.0499 and Power equal to 0.9065. If the true ORR is 40%, the probability of rejecting the hypothesis at each evaluation of the stopping rules varies, but cumulatively is 0.0935. If the true ORR is 40% and $N=45$, the exact 95% confidence interval (Clopper-Pearson) around the point estimate for ORR will be (25.7, 55.7). If the outcome in a treatment arm is promising and the option is taken to enroll up to 100 patients in the mITT in a specific treatment arm (45 patients in the initial arm plus 55 patients), to narrow the confidence interval around the ORR point estimate and to increase the size of the safety database, the exact 95% confidence interval around a true ORR of 40% will be (30.3, 50.3). Data collected in patients enrolled beyond the planned Phase 2 sample size will be used in secondary and supportive analyses. The primary analysis includes independent

evaluation of each of the four treatment arms in the first 45 patients; study expansion enables confirmation of the results of the primary analysis. The use of the Bayesian Predictive Probability Design within each arm effectively controls the overall Type I error to a maximum of 5% for each population of interest.

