9.4 Efficacy Endpoint Definitions and Analyses

9.4.1 Objective Response Rate

Objective disease response will be categorized in accordance with RECIST v1.1 (Appendix 2). Objective Response Rate (ORR) is defined as the percent of patients documented to have a confirmed Complete Response (CR) or Partial Response (PR), as reported by the central review laboratory. The primary analysis will be conducted approximately 12 weeks after the last patient is enrolled, allowing for observation of an early disease response and confirmation of PR or CR. ORR as reported by the investigator in the CRF will be used in secondary and supportive analyses as well as by the Internal Data Monitoring Committee for purpose of decision making using the Bayesian Predictive Probability Design.

Descriptive statistics (frequency and percentage) for ORR, CR, and PR will be presented. The exact 95% confidence interval of these response rates will be constructed. An exact test for single proportion (two-sided $\alpha=5\%$) will be performed to test $H_0: ORR \leq 20\%$ against $H_1: ORR > 20\%$. Other details will be described in the SAP.

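### Section 9.1 declares an arm efficacious at 14/45, but the exact test in Section 9.4.1 of the same null first rejects at 15/45, and the plan does not say which rule governs.

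*Combined protocol and SAP*

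**What the plan says.** The Study Summary (Statistical Considerations) and Section 9.1 give a success rule for each arm: "if more than 13 responses are observed among the first 45 patients enrolled who meet the criteria for the mITT population", then "the drug will be declared efficacious". Section 9.1 attaches operating characteristics to that rule: "The Type 1 error is equal to 0.0499 and Power equal to 0.9065". Both places set the design constraints as type I error below 0.05 and power of at least 0.90, for a null ORR of 20% and a target of 40%.

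Section 9.4.1 sets a second procedure: "An exact test for single proportion (two-sided $\alpha=5\%$) will be performed to test" ORR of at most 20% against ORR above 20%, with an exact 95% confidence interval. On the rest it says: "Other details will be described in the SAP".

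Both procedures address the same patients, because Section 9.1 describes the primary analysis as an independent "evaluation of each of the four treatment arms in the first 45 patients".

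The response data are divided by role. Section 9.4.1 defines ORR by confirmed central review. It uses investigator-reported ORR in secondary and supportive analyses, "as well as by the Internal Data Monitoring Committee for purpose of decision making using the Bayesian Predictive Probability Design". The Study Design text in the Study Summary and Section 9.9 make the same division.

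**The concern.** One null hypothesis, in one set of 45 patients, has two decision rules with different cut-offs. An arm that finishes on exactly 14 responses would be efficacious under 9.1. Under 9.4.1 it would be non-significant, with a confidence interval that includes the rate the plan calls uninteresting. The stated power also attaches to only one of the rules. If the exact test is the primary inference, the plan misses its own power requirement.

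The Study Summary and Section 3 foresee an accelerated approval application based on one or more arms. The criterion for success should therefore not be left to be chosen after the count is known.

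**Working it through.** **Inputs** (Section 9.1): null 20%, target 40%, N = 45 per arm; stops at 0/10, 1/14, 2/18, 3/22, 4/26, 5/29, 6/32, 7/35, 8/37, 9/39, 10/41, 11/43, 12/44 and 13/45; success at 14 or more. From Section 9.4.1: exact test, two-sided 5%.

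**1. Reproduce the plan's figures.** Let f(n, k) be the probability of being unstopped with k responses after n patients in enrolment order. Then f(n, k) = (1 − p) f(n − 1, k) + p f(n − 1, k − 1). At each listed n, every k at or below the boundary is removed. Success is the sum of f(45, k) over k ≥ 14.

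- At p = 0.20: success 0.0499, early termination 0.9199, expected N 28.3.
- At p = 0.40: success 0.9065, cumulative stopping 0.0935.

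These match the stated 0.0499, 0.92, 28, 0.9065 and 0.0935.

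**2. Apply the 9.4.1 test.** The upper tail is P(X ≥ r) for X ~ Binomial(45, 0.20). The two-sided p-value is shown by minimum likelihood and by doubling that tail; the interval is Clopper-Pearson.

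| Result | Upper tail | Two-sided p (min. likelihood / doubled) | 95% CI | Rejects? |
|---|---|---|---|---|
| 13/45 | 0.0995 | 0.138 / 0.199 | 16.4% to 44.3% | No |
| 14/45 | 0.0521 | 0.090 / 0.104 | 18.2% to 46.6% | No |
| 15/45 | 0.02499 | 0.038 / 0.04999 | 20.0006% to 48.95% | Yes |

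Both p-value methods and the interval give 15 as the first rejecting count.

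**3. Would a one-sided 5% exact test align the rules?** No: at 14/45 its p-value is 0.0521, above 0.05. The 0.0499 in 9.1 is lower because it credits the futility stops. The difference, 0.0521 − 0.0499 = 0.0022, is the chance under the null of crossing a stop on a path that would still have reached 14. A fixed-sample test has no such credit.

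**4. Operating characteristics of each cut-off, with the listed stops on the same responses.**

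| Success at | Type I error (20%) | Power (40%) |
|---|---|---|
| ≥14/45 | 0.0499 | 0.9065 |
| ≥15/45 | 0.0245 | 0.8507 |

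Without stops, ≥15/45 gives 0.02499 and 0.857, and ≥14/45 gives 0.0521 and 0.9164.

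**5. Size of the conflict.** The rules disagree only at exactly 14/45. With the stops, that has probability 0.9065 − 0.8507 = 0.0558 at 40% and 0.0499 − 0.0245 = 0.0254 at 20%. The same recursion gives 0.1183 at 30%.

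**The case against.** The strongest reply is that the plan already separates the two procedures: the Bayesian design is an enrolment tool run by the IDMC on investigator data, and the exact test is the primary analysis on central data. Much of this stands. Section 9.4.1, Section 9.9 and the Study Design text all support the division, so it would be wrong to say that the plan is silent on data source. What remains is that the efficacy declaration in the Study Summary and 9.1 is not confined to enrolment decisions. Section 9.1 words it as a conclusion about the drug, gives it a type I error and power, and in the same paragraph describes the primary analysis.

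A second reply is that the SAP or the IDMC charter may settle precedence. That is possible, since neither text is available here, and the finding is limited accordingly. The threshold arithmetic does not depend on it.

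A third reply is that only one count is affected and no stated figure is wrong. Both are true, and they limit the weight of the point.

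A reader might go further and infer that 0.0499 and 0.9065 are errors. They are not: both reproduce exactly. A reader might also infer that type I error for the 14/45 rule can never exceed 0.0521. That holds only for a fixed set of 45 patients, and Section 9.9 lets the IDMC apply the design to patients on the tablet formulation alone. Nor can the effect of disagreement between investigator and central reads be sized, because the plan expects some but gives no figure.

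**Conclusion.** The concern holds as a conflict between two rules, and the supplied text does not resolve it. Followed as written, 9.1 and 9.4.1 give opposite conclusions at exactly 14/45: 5.6% of the time per arm at a true ORR of 40%, 11.8% at 30% and 2.5% at 20%. The more general consequence is that the stated power of 0.9065 does not describe the exact test. That test's power at 40% is 0.851 with the listed stops, or 0.857 without, against a requirement of at least 0.90.

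These probabilities assume that the stops and the final count use the same responses, in enrolment order. The first rejecting count of 15 needs no such assumption and is the same under either p-value method. The weight is minor to moderate, but the matter should be settled before the counts are known.

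**What to change.** State in the Study Summary, 9.1 and 9.4.1 which rule decides the efficacy declaration and on which response data. Name the exact p-value method in either case.

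- **(a) If the 9.1 rule governs:** label the 9.4.1 test and 95% interval as supportive, and note that the interval at 14/45 includes 20%. State that 0.0499 and 0.9065 hold only when the stops and the final count use the same responses in enrolment order. If the final count is central, add that type I error can reach 0.0521 for a fixed set of 45 patients, which exceeds the constraint of below 0.05, so that constraint needs amending too. Add that power may fall below 0.90 where the two reads disagree; the margin is only 0.0065.
- **(b) If the 9.4.1 test governs:** set success at 15/45 or more and keep the earlier stops. Restate type I error as 0.0245 and power as 0.851, on the same condition about responses and order, and amend the 0.90 power constraint in the Study Summary and 9.1.

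Option (a) costs a few sentences, plus an amended type I error constraint if the final count is central. Option (b) costs a changed cut-off, restated figures and an openly lower power. Neither needs new boundaries or more patients.

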9.4.2 Duration of Response

Duration of Response (DR) is defined as the time from date of the first documentation of objective tumor response (CR or PR) to the first documentation of Objective Progression of Disease (PD) or to death due to any cause in the absence of documented PD.

Censoring for the DR endpoint will be assigned on the date of the last tumor assessment if no assessment of tumor progression is identified by the central radiology review and the patient does not die while on study. DR will only be calculated for the subgroup of patients with an objective response. The Kaplan-Meier method will be used to obtain the estimate of median DR.

9.4.3 Progression Free Survival

Progression-free survival (PFS) is defined as the time from date of first study treatment to first PD or death due to any cause in the absence of documented PD. Censoring for the PFS endpoint will be assigned on the date of the last tumor assessment if no assessment of tumor progression is identified by the central radiology review and the patient does not die while on study. For patients in whom two or more sequential assessments are missed, followed by the finding of tumor progression, the PFS endpoint will be censored on the date of the last tumor assessment before the gap. Patients lacking an evaluation of disease after first study treatment will have their PFS time censored on the date of first dose with duration of 1 day. Patients who start a new anti-cancer therapy prior to documented PD will have the endpoint censored at the date of the last tumor assessment prior to the start of the new therapy. The Kaplan-Meier method will be used to obtain the estimate of median progression-free survival time.

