9.2 Data Handling

Listings of all patient data will be prepared. Data summaries will be presented in tabular and/or graphical format and summarized descriptively, by the four groups of patients having genetic tumor alterations activating *MET*, where appropriate. If some (or all) of those four groups of patients show similar objective response rate, data summaries (efficacy and safety) will also be presented for those groups combined as supportive analyses. Response rates will be considered similar between groups, if they are within $\pm 10\%$. Further details of planned analyses will be described in the SAP.

For all variables, only the observed data from patients will be used in the statistical analyses; there is no plan to estimate missing data. Patients without a valid clinical response assessment will be assigned a best overall response of not evaluable (NE). Data from patients who are lost to follow-up or have missing observations before reaching an endpoint in any of the time-to-event analyses will be treated as censored with specific rules defined in the SAP.

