Potential exists for individual tumor lesions to develop necrosis, to cavitate, have a flair response to treatment or become otherwise difficult to evaluate for a period of time as the result of beneficial study treatment impact. For example, tumor necrosis, cavitation or flair may result in increase in overall size of individual lesions or unclear tumor margins prior to recovery to smaller lesions, development of scar tissue, or complete resolution. The true tumor measurements of lesions should be recorded but the conclusion of progressive disease may be suspended until continued assessment clarifies the nature of the tumor change. If repeat assessments indicate progression of disease, then PD should be recorded on the date of the first assessment giving the impression of progression. If repeat assessments indicate that the change was a process of transition, then NE (not evaluable) should be recorded during the period of transition, and PR or CR may be recorded for subsequent evaluations. The CRF will collect information on the observations during the period of transition to support the assessment conclusions.

Supplemental Investigations

If CR determination depends on a residual lesion that decreased in size but did not disappear completely, it is recommended the residual lesion be investigated with biopsy or fine needle aspirate. If no disease is identified, objective status is CR.

Best Objective Response

Target Lesions	Non-Target Lesions	New Lesion	Point in Time Response	Best Response
CR	CR	No	CR	CR and PR require confirmation at least 4 weeks after first observation
CR	Non-CR/Non-PD	No	PR	
PR	Non-PD	No	PR	
SD	Non-PD	No	SD	SD requires an on-study assessment after at least 6weeks on treatment. Unconfirmed PR or CR are reported as SD.
PD	Any	Yes or No	PD	
Any	PD	Yes or No	PD	
Any	Any	Yes	PD	

Subjective Progression

Patients requiring discontinuation of treatment due to worsening health status attributable to advancement of the malignancy under study but without objective evidence of disease progression should not be reported as PD on tumor assessment CRFs. This should be indicated on the end of treatment CRF as off treatment due to Global Deterioration of Health Status.

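### The PFS missed-scan rule in 9.4.3 censors progression found after a gap but by default counts a death after the same gap on the death date, which tends to lengthen PFS

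*Combined protocol and SAP*

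**What the plan says.** Under 9.4.3 the PFS clock runs from first study treatment to "first PD or death due to any cause in the absence of documented PD". Nothing limits the time between the last scan and the death.

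The same section then gives four censoring rules:

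- The general rule censors at the most recent scan, and applies only "if no assessment of tumor progression is identified by the central radiology review and the patient does not die while on study".
- The gap rule covers the case where "two or more sequential assessments are missed, followed by the finding of tumor progression, the PFS endpoint will be censored" at the last assessment before the gap. Death is not named.
- Patients without any post-baseline scan are handled separately: "Patients lacking an evaluation of disease after first study treatment will have their PFS time censored on the date of first dose".
- So are those who change treatment: "Patients who start a new anti-cancer therapy prior to documented PD will have the endpoint censored", at the last assessment before the new therapy.

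Section 9.2 deals with loss to follow-up and incomplete data in general terms: "missing observations before reaching an endpoint in any of the time-to-event analyses will be treated as censored with specific rules defined in the SAP". I find no rule for death after a gap in the supplied text.

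Three other parts of the protocol matter here:

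- Section 7.3 schedules scans every 6 weeks to about one year and every 12 weeks afterwards. Two missed scans therefore leave more than 12, later more than 24, weeks unobserved.
- Sections 6.4 and 7.6 follow survival every two months after treatment.
- Appendix 2 says that patients stopping for worsening health "without objective evidence of disease progression should not be reported as PD on tumor assessment CRFs".

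**The concern.** Two patients with identical missing imaging are treated in opposite ways. If progression is found when imaging resumes, the patient leaves the risk set at the last scan. If the patient dies instead, the whole unobserved interval counts as progression-free. The death is certain, but it does not show that the patient was free of progression until then.

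The protocol makes this case plausible. A patient who deteriorates and is not scanned cannot be recorded as PD, yet survival contact will capture the death. A patient whose investigator-assessed progression is not confirmed centrally may be in the same position, because 7.3 ends scheduled imaging at investigator progression while PFS rests on central review. Section 9.4.3 does not say whether scans no longer scheduled count as missed.

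PFS by central review is a named secondary endpoint in a study that may support an accelerated approval application (section 3). There is no control arm in which such a bias could cancel.

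**Working it through.** **Plan's own figure.** None exists. The plan gives no assumed median PFS, event count, PFS power or missed-scan rate. What follows is a reading of the rules plus illustrations on stated assumptions.

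**Step 1: small Kaplan-Meier example.** Ten patients. Eight have events at weeks 6, 12, 18, 18, 24, 30, 36 and 48, and one is event-free beyond week 48. The tenth is last scanned at week 12 and misses weeks 18 and 24.

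| Tenth patient | Handling | S(24 weeks) |
|---|---|---|
| PD found at week 30 | censored at week 12 | 0.8 × 5/7 × 4/5 = 0.457 |
| Dies at week 30 | event at week 30 | 0.8 × 6/8 × 5/6 = 0.500 |
| Either, dated at first missed scan | event at week 18 | 0.8 × 5/8 × 4/5 = 0.400 |

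If the unseen progression fell between weeks 12 and 18, complete imaging would give 0.400, and the death rule overstates by 0.100. If it fell between weeks 24 and 30, complete imaging would give 0.500, and dating at week 18 understates by 0.100.

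By week 30 the order against censoring reverses. The death rule gives 0.500 × 3/5 = 0.300; censoring gives 0.457 × 3/4 = 0.343. Compared with censoring, counting the death raises the curve before it and can lower it afterwards.

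**Step 2: illustrative size.** Assumed, not from the documents: exponential times with median 20 weeks to progression and a further 20 weeks to death; 10, 20 or 30% of patients stop imaging after at least one post-baseline scan; no new therapy. From 7.3: the scan schedule. Change under the rule as written, against complete imaging:

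| Affected | 52-week restricted mean | Median |
|---|---|---|
| 10% | +0.6 to 0.9 weeks | 0 |
| 20% | +1.2 to 1.9 weeks | 0 |
| 30% | +1.9 to 2.8 weeks | 0 to +5 weeks |

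The median is insensitive because progression is seen only at scans. With a true median of 20 weeks, the progression-free proportion is 0.5^(18/20) = 0.536 at week 18 and 0.5^(24/20) = 0.435 at week 24. The observed median is therefore week 24, and S(24) must rise by more than 0.500 − 0.435 = 0.065 before it moves.

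**Step 3: is the direction stable?** A wider grid of 24 scenarios used median 16 or 26 weeks to progression; 8, 20 or 36 weeks from progression to death; 10 or 30% affected; and last scan just before progression or at random.

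- Against complete imaging, the rule as written gave a longer restricted mean in all 24: by 0.37–1.09 weeks at 10% and 1.15–3.40 weeks at 30%. Part of this comes from deaths before the second missed scan, which no gap rule reaches.
- Against censoring deaths after a gap, it was longer in 22 of 24, by up to 1.57 weeks, and shorter by 0.06 and 0.23 weeks in the other two.

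**Step 4: how much does symmetric censoring remove?** Restricted means in weeks, 30% affected:

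- Medians 16 and 20, last scan just before progression: complete 23.25, as written 26.06, both censored 25.44. Removed: 0.62 of 2.81, or 22%.
- Same medians, last scan at random: 23.10, 25.79, 24.34. Removed: 1.45 of 2.69, or 54%.
- Medians 20 and 20, last scan just before progression: 26.5, 29.3, 28.9. Removed: 0.4 of 2.8, or 14%. Dating at the first missed scan gave 26.6, removing 2.7 of 2.8.

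**The case against.** The strongest reply is that the text is not settled. Section 9.2 can be read as censoring these patients and defers the details to the SAP. The general rule also depends on death *while on study*, which is undefined. Sections 6.4 and 7.6 describe treatment given in survival follow-up as coming after study participation, so a death in that period might not be on study and would be censored at the last scan. Section 9.4.4 points the other way by calling survival follow-up on-study. This stands as a reason to call the asymmetry the default reading. It does not supply a rule that removes it, and it shows that 9.2 and 9.4.3 need reconciling.

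The affected group is also limited. New therapy and absence of any post-baseline scan both lead to censoring, and stopping scans before progression departs from 7.3. This stands too, and the illustration is restricted accordingly.

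The consequence is modest. PFS is secondary, with no test or threshold. With 45 patients in an arm, a simulated median spans roughly 18 to 36 weeks at 10–20% affected under either rule. That limits the importance of the point, but a bias with a predictable direction is still worth closing before data are seen.

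A reader might infer that 9.4.2 has the same fault. It does not: duration of response has no gap rule, so progression and death after a gap both count there. A reader might also argue a departure from standard convention. The documents set out no such convention, so the point rests on the internal inconsistency alone.

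**Conclusion.** The point holds. As worded, 9.4.3 by default treats equal gaps unequally, and for untreated imaging dropouts with at least one post-baseline scan this tends to lengthen PFS. The direction against complete imaging was the same in every scenario tried. The size cannot be computed from the documents. Under the 20-and-20-week assumption it is under a week of 52-week restricted mean at 10% affected and about two to three weeks at 30%.

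A reader might infer that median PFS is inflated by several weeks even at moderate dropout. The illustration does not support that: the median moves only at 30%, and then by at most about 5 weeks. Nor does censoring both outcomes cure the problem. It is itself informative and removed between 14% and 54% of the excess in the runs shown.

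ORR, the stopping rules, sample size and error rates do not depend on PFS and are unaffected.

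**What to change.** 1. In 9.4.3, extend the gap rule so that it reads *followed by tumor progression or death*, with both censored at the last assessment before the gap.
2. State whether deaths in survival follow-up are on study for PFS, and make 9.2 agree with 9.4.3.
3. Add a sensitivity analysis that dates both progression and death after such a gap as events at the first missed scan. It may somewhat shorten PFS if patients stop imaging well before progression, so the two results roughly bracket the effect.

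Leave 9.4.2 as it is.

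The cost is a few sentences, one extra analysis and some more censored patients. Section 9 allows the SAP to modify such plans; a protocol amendment is required only for major changes to the primary endpoint or its analysis.
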